Management of Sub-Clinical Bacteriuria in Pregnancy: A Feasibility Trial

NCT03275623

Version Date: 08/22/2017

Management of Sub-Clinical Bacteriuria in Pregnancy: A Feasibility Trial

[name]
[name]
[name]
[name]

Background:

Bacterial Colonization in the Urine

Assessment and treatment of bacterial colonization in the urine during pregnancy is a routine part of prenatal care.¹ A urinary tract infection (**UTI**) is defined as urine culture colonization >100,000 (**10⁵**) colony forming units (**CFU**) of bacteria per ml with signs and symptoms of UTI including dysuria, frequency, urgency, suprapubic pain, and/or hematuria.¹⁻³ Asymptomatic bacteriuria (**ASB**) is defined as urine culture colonization > 10⁵ CFU in the absence of signs and symptoms of UTI, and occurs in 2-10% of pregnancies.^{3,4} Pregnant women with a UTI or ASB are routinely prescribed antimicrobial therapy based on identified organisms and sensitivities.

Sub-Clinical Bacteriuria

Sub-clinical bacteriuria (**SCB**) occurs when urine culture colonization is between 1 - 10⁵ CFU. The frequency by which SCB occurs in pregnancy is unknown. It is also unknown the rate of progression from SCB to UTI and/or ASB, and subsequently development in to pyelonephritis. Moreover, there are no current guidelines that direct management in this particular condition in pregnancy. In current clinical practice, there is strong variation in care such that many patients are treated, despite the lack of proven benefit while other clinicians do not treat.

[figure not shown]

Figure 1. Schematic of potential progression of bacterial colonization in the urine.

Clinical Importance

Bacterial colonization in the urine during pregnancy can lead to adverse maternal and neonatal outcomes. Pyelonephritis is the primary concern in pregnancy due to its association with potential urosepsis, renal abscess, decline in renal function, preterm labor and preterm birth.⁵ Although untreated

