UTI is the greatest risk factor for developing pyelonephritis, ASB can also lead to pyelonephritis. In a recent randomized controlled trial of 4200 women in the Netherlands, they report that the incidence of pyelonephritis is only 2.4% when ASB is untreated compared to 0.6% when treated.⁶ With such a low incidence, there is new debate whether to treat or expectantly manage ASB. This same debate also pertains SCB. It is unknown whether treatment or expectant management of SCB will lead to difference in the rate of progression to UTI and/or SCB, and ultimately pyelonephritis.

Risk of Antimicrobial Therapy

The two main risks of empiric antimicrobial therapy include potential for adverse drug effects and contribution to drug resistance. The use of antibiotics is not benign especially during pregnancy. Adverse drug effects include masking a diagnosis with empiric treatment of symptoms and no identification of an organism. Often times the diagnosis maybe correct, but the antibiotic that was chosen for treatment does not have sufficient coverage of the organism that is causing the infection. Common side effects to routinely used antibiotics such as nitrofurantoin, sulfa, amoxicillin and cephalixin includes rash and diarrhea.⁹⁻¹⁰ The rise in antibiotic resistance over the past decades is evidence to the clinical consequences of unnecessary antimicrobial treatment across the disciplines in medicine. Such consequences also have been evident in the field of obstetrics. Nearly 50% of urinary isolates are resistant to routine ambulatory antibiotic therapy. Zhanel et al. looked at resistance to treatment in the NAUTICA trial. The goal of the North American Urinary Tract Infection Collaborative Alliance (NAUTICA) study was to determine antibiotic susceptibility to commonly used agents for urinary tract infections against outpatient urinary isolates obtained in various geographic regions in the USA and Canada. This study reports higher rates of antibiotic resistance in US versus Canadian outpatient urinary isolates and demonstrates the continuing evolution of resistance to antimicrobial agents.⁷ Thus, if antibiotic therapy is not necessary for the management of subclinical cystitis due to low incidence of progression to pyelonephritis, it should not be prescribed.

Gap in Knowledge

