The gap in knowledge is whether the risks and benefits of empiric treatment with antimicrobial therapy for treatment of SCB outweigh the risk and benefits of developing UTI, ASB or pyelonephritis from expectant management or no treatment of SCB.

Rationale for this clinical trial

The rationale for this clinical trial is to determine if treatment of urine cultures with organisms of 1 – 100,000 CFU are beneficial to pregnancy outcomes when obtained at routine prenatal clinic visits. In current clinical practice, there is a strong variation in care such that many patients are treated for urine cultures with organisms of $<10^5$ CFU despite the lack of proven benefit while other clinicians do not treat.

If it is found that treatment of urine cultures with 1 - 10^5 CFU impact clinical care of a pregnant patient by decreasing adverse pregnancy outcome, guidelines will need to be modified to include treatment recommendations of urine cultures that do not currently meet criteria of a urinary tract infection. On the other hand, if there is no benefit to treatment of urine cultures 1 - 10^5 CFU, then unnecessary antibiotics could be avoided thereby potentially reducing unknown adverse effects to these drugs or resistance to antibiotics, which continues to be an alarming health challenge.

Hypothesis:

We hypothesize that treating urine cultures with organisms between 1- 10^5 CFU grown in culture media in a pregnant population leads to improvement of pregnancy outcomes.

Objectives:

To determine the rate of progression from SCB to either UTI or ASB with antimicrobial treatment of urine cultures with organisms of $1-10^5$ CFU compared to no treatment at prenatal care clinic visits.

Study Design:

For this pilot study, we propose a feasibility trial to determine if a randomized control trial for the treatment of subclinical cystitis to prevent pyelonephritis and culture proven cystitis. The trial will investigate the effects of treatment or non-treatment of urine cultures obtained during prenatal care visits prompted by a positive urinalysis or symptoms, and determine if a randomized control trial is needed to further investigate outcomes.

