At the initial prenatal care clinic visit all pregnant women will have their urine screened with a UA and urine culture. Patients meeting inclusion criteria will be approached for randomization.

Those with a urine culture positive for bacteria 1- 10x5 CFU will be randomized to treatment or no treatment.

Those randomized to NO treatment will have a test of cure performed three weeks after initial negative urine culture or at next clinical visit thereafter.

Those randomized for treatment will be prescribed the most commonly used antibiotic for urinary tract infections in pregnancy. This includes: Nitrofurantoin, Cephalexin, and Amoxicillin. It is unsure which antibiotic the participant will receive but a majority of the time it will be one of the above named antibiotic. The choice will be determined by the physician, but will accommodate participants' prior medication history and adverse events.

Treatment will continue with a test of cure (urine culture performed after treatment with antibiotics) after each round of antibiotic until the urine culture shows no growth of bacteria and/or shows any amount of skin flora only.

Written, informed consent will be obtained by a member of our research team, either a physician or research assistant.

Once the patient is randomized to their designated arm, urine cultures will continue to be collected throughout prenatal care visits as clinically indicated.

[figure not shown]

Figure 2. Flow diagram of study

Primary Outcome:

The incidence of cystitis defined as a urine culture with $>10^5$ at any point during antenatal care in this pregnancy population and the incidence of pyelonephritis.

Data Collection:

Data will be collected using standardized forms regarding maternal demographics, pregnancy characteristics, laboratory tests ordered in response to clinical signs or symptoms, medications prescribed and/or administered, and maternal/fetal adverse effects. Information for these forms will be obtained from UTPB and Bellaire clinical schedule, Care4 and AllScripts. The standardized forms that will be used during the study have been developed and approved by the Department of Obstetrics, Gynecology, and Reproductive Sciences for the purposes of uniform data collection of Internal Review Board approved studies being conducted.

Sample Size:

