Because this is a feasibility trial, 50 patients will be recruited from all clinical sites. 25 patients will be randomized to prenatal care with treatment for any urine culture with growth between $1-10^5$ CFU of any organism and 25 patients will be randomized to prenatal care without treatment for any urine culture with growth between $1-10^5$ CFU of any organism. Recruitment will be stopped after recruitment of 50 randomized patients or a 10-month time period whichever is completed first.

Data Analysis

Chi-square tests will be used to compare categorical data between the two treatment groups. Student's t-test will be used to compare numerical data. The rate of progression to SCB, UTI, or pyelonephritis will be determined by clinical findings, diagnosis if admitted to the hospital and laboratory/urine culture results meeting criteria for those mentioned above.

Procedures to Maintain Confidentiality

All information and data will be kept on paper research charts that will be stored in a locked file cabinet within a locked research office of our research team/research coordinator. In addition, an electronic database of information and data will be stored on the computer of our research coordinator that is password protected, and in a locked office of the research coordinator. We will record subject information only by study code number.

Potential Benefits and Risks

There are potential risks and benefits to either treatment strategy. Since treatment or no treatment are currently both generally accepted standard of care options, providers, based on their personal preference and practice style, may choose to treat or not. Potential benefits of antibiotic treatment of those with $1-10^5$ CFU in urine culture may be decreased development of UTI, pyelonephritis, PTL, and preterm birth. Potential risks of treatment may be side effects of the medications as well as potential untoward effects of antibiotic therapy that may increase development of resistant organisms in urine and other locations (e.g. vaginal, cervix, gut) or may lead to change in flora (e.g. vaginal, cervix, gut) which may increase risk of adverse pregnancy outcomes. The benefits of no treatment may be to avoid unnecessary and unindicated antibiotic therapy. If evidence shows that treatment of this subset of

pregnant patients decreases adverse pregnancy outcome, this can leave a lasting impact on how we treat urinary tract infections in pregnancy.

References

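### Pyelonephritis is an unranked primary outcome compared by chi-square, but 50 women cannot inform on it: zero or one case is likely whether or not treatment works

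*Combined protocol and SAP*

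**What the plan says.** The Primary Outcome section gives two outcomes in one sentence: cystitis, meaning a culture above 10^5, "at any point during antenatal care in this pregnancy population and the incidence of pyelonephritis". Neither is ranked above the other, and no rule says which one decides.

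The Objectives section is narrower. Its aim is "To determine the rate of progression from SCB to either UTI or ASB with antimicrobial treatment", compared with no treatment. The Study Design section, however, names prevention of both pyelonephritis and culture-proven cystitis.

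The size is fixed in the Sample Size section: "Because this is a feasibility trial, 50 patients will be recruited from all clinical sites". Of these, "25 patients will be randomized to prenatal care with treatment" and the same number without it. Recruitment also stops at 10 months if that comes first. No alpha, power, target difference or expected event count is stated. The Data Analysis section applies chi-square tests to categorical data between the arms.

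The only pyelonephritis rates are in Clinical Importance, which cites a trial reporting that "the incidence of pyelonephritis is only 2.4% when ASB is untreated compared to 0.6% when treated". For the trial's own population the Sub-Clinical Bacteriuria section says: "It is also unknown the rate of progression from SCB to UTI and/or ASB, and subsequently development in to pyelonephritis".

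Under Risk of Antimicrobial Therapy the plan reasons that "if antibiotic therapy is not necessary for the management of subclinical cystitis due to low incidence of progression to pyelonephritis, it should not be prescribed". The Rationale section adds that antibiotics could be avoided if treatment shows no benefit.

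**The concern.** A primary outcome should be able to look different when treatment works and when it does not. If pyelonephritis is so rare that 50 women will most often yield zero cases or one under either state of affairs, the comparison answers nothing, and the planned test cannot be relied on at such counts.

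What is at stake is interpretation. A near-empty table under a primary heading invites the reading that progression is rare and treatment unnecessary, and the background already supplies that line of reasoning. The plan itself calls pyelonephritis the main concern in pregnancy, so unfounded reassurance would matter. Nothing in the Data Analysis section guards against it.

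**Working it through.** **Inputs.** 25 women per arm (Sample Size). Pyelonephritis rates of 2.4% untreated and 0.6% treated (Clinical Importance); these are ASB rates and serve only as a proxy for SCB. Assumed because the plan is silent: no dropout, full recruitment, two-sided 0.05 for any test.

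**The plan's own figure.** N = 50 rests on feasibility alone. The only check available is 25 + 25 = 50, which agrees. There is no power or precision calculation to reproduce.

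**1. Expected cases at the proxy rates.** 25 × 0.024 = 0.60 untreated; 25 × 0.006 = 0.15 treated; total 0.75.

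**2. Chance of few cases at the proxy rates.**
- No case: 0.976^25 × 0.994^25 = 0.545 × 0.860 = 0.469.
- At most one: 0.469 × (1 + 25 × 0.024/0.976 + 25 × 0.006/0.994) = 0.469 × 1.766 = 0.828.

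**3. The same if treatment does nothing and both arms run at 2.4%.** Expected cases: 50 × 0.024 = 1.2. No case: 0.976^50 = 0.297. At most one: 0.297 × (1 + 50 × 0.024/0.976) = 0.297 × 2.230 = 0.662. Two or more cases therefore have about a one-in-three chance.

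**4. Sensitivity to the proxy, in both directions.** Multiply both rates by m and repeat steps 1 and 2.

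| m | Expected cases | No case | At most one |
|---|---|---|---|
| 0.5 | 0.375 | 0.988^25 × 0.997^25 = 0.686 | 0.686 × (1 + 25 × 0.012/0.988 + 25 × 0.003/0.997) = 0.95 |
| 1 | 0.75 | 0.469 | 0.83 |
| 2 | 1.5 | 0.952^25 × 0.988^25 = 0.216 | 0.216 × (1 + 25 × 0.048/0.952 + 25 × 0.012/0.988) = 0.55 |

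The expected total passes one case when m exceeds 1/0.75 = 1.33.

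**5. What zero cases would show.** The exact two-sided 95% upper limit for 0/25 is 1 − 0.025^(1/25) = 0.137, which is 13.7/2.4 = 5.7 times the quoted untreated rate. Pooling both arms, 0/50 gives 1 − 0.025^(1/50) = 0.071.

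**6. The planned test.** With no case in either arm, the chi-square statistic is undefined. With one case in total, the expected count in each event cell is 0.5, far too small for the approximation. With no treated cases, the uncorrected test gives p = 0.074 for three untreated cases and p = 0.037 for four, so at least four are needed. By exact enumeration, its power at 2.4% versus 0.6% is 0.24%. For scale, 80% power for that difference would need 715 per arm, or 1,430 in total (normal approximation, no continuity correction).

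**The case against.** The strongest reply is that this is a pilot. The Study Design section says it will help decide whether a randomized trial is needed, and the sample size is set on that ground, so nobody should expect it to settle pyelonephritis. This softens the risk of misreading. It does not remove it: the plan names no feasibility outcome, makes clinical events primary, states an efficacy hypothesis and compares the arms by chi-square.

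Several stronger readings are tempting, and the documents do not support them:

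- A reader might infer that the plan predicts under one case, or that the ASB rates are a ceiling for SCB. The plan calls the SCB rate unknown. Some women are cultured because of symptoms, whereas ASB is by definition symptom-free, so the true risk could be higher or lower.
- A reader might infer that the plan commits to withholding antibiotics if pyelonephritis is rare. That sentence is conditional background on antibiotic risk and does not set a decision rule for this trial.
- A reader might infer that pyelonephritis entered the primary outcome with no basis elsewhere. The Study Design and Gap in Knowledge sections both name it; the Objectives sentence is the narrower one.
- A reader might infer that diagnosis rests on clinical impression by physicians who know the arm. The Data Analysis section also lists hospital diagnosis and "laboratory/urine culture results meeting criteria for those mentioned above", and no section says who classifies cases. The text gives no pyelonephritis criteria, but that is a missing detail and a separate matter.

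It is also fair to say that cystitis shares the primary position. The document gives no rate for it, so nothing here shows whether 25 per arm is enough for that outcome.

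**Conclusion.** The concern holds for the pyelonephritis component only. At the document's ASB rates, 0.75 cases are expected in total, with a 47% chance of none and 83% of at most one. With no treatment effect at 2.4% in both arms, 1.2 cases are expected and at most one still has a 66% chance. The two situations therefore produce largely overlapping results. Zero cases in an arm would be compatible with a true rate as high as 13.7%, and the chi-square test is invalid at these counts.

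The exact figures depend on the proxy rates, full recruitment and no dropout. The conclusion does not depend on them closely: at half the rates the chance of no case is 69%, and at twice the rates 1.5 cases are expected and the chance of none is 22%. Stopping at 10 months could only reduce the numbers. The sample size of 50 is not an arithmetic error; the difficulty is pairing it with this outcome as a compared primary endpoint.

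**What to change.** Amend the Primary Outcome and Data Analysis sections as follows.

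- Keep culture-defined progression (above 10^5) as the primary clinical outcome, in line with the Objectives section.
- Make pyelonephritis a descriptive secondary or safety outcome, reported as a count per arm with exact (Clopper-Pearson) 95% limits and no chi-square test.
- State that few or no cases will not be taken to show that treatment is unnecessary.

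The cost is amendment wording, with no extra patients or procedures. The downside is that the trial gives up a headline comparison on pyelonephritis, one that its size cannot support. The change does not make 25 per arm adequate for the progression outcome, so a null result there needs the same restraint.

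### Cystitis and pyelonephritis incidences are compared between arms only by chi-square at 25 per arm at most, with no planned effect measure or confidence interval

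*Combined protocol and SAP*

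**What the plan says.** All references are to the combined protocol and SAP.

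- **Primary Outcome** names the incidence of cystitis (a culture above 10^5) "at any point during antenatal care in this pregnancy population and the incidence of pyelonephritis". No composite is defined, so I read these as two binary outcomes. The heading is singular, but the gap is the same under either reading.
- **Data Analysis** has three sentences. The first is "Chi-square tests will be used to compare categorical data between the two treatment groups". The second gives Student's t-test for numerical data. The third begins "The rate of progression to SCB, UTI, or pyelonephritis will be determined by clinical findings" and describes how events are ascertained. It implies a rate in each arm, but no contrast between arms. The section does not say whether chi-square carries a continuity correction, and states no alpha.
- **Objectives** is comparative: "To determine the rate of progression from SCB to either UTI or ASB with antimicrobial treatment of urine cultures", set against no treatment.
- **Study Design** says the trial should "determine if a randomized control trial is needed to further investigate outcomes".
- **Sample Size** gives 25 per arm on feasibility grounds, with an earlier stop possible: "Recruitment will be stopped after recruitment of 50 randomized patients or a 10-month time period whichever is completed first".

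No section names a risk difference, risk ratio, odds ratio, confidence interval or exact test.

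**The concern.** The stated aims are matters of estimation: how far progression differs between the arms, and whether a larger trial is worth running. A chi-square p-value answers neither. In a trial this small, a non-significant result is the likely outcome whatever the truth, and it is easily read as no effect. For a rare outcome the test may return nothing at all. An interval would show which effects remain compatible with the data, which is what the planners of a larger trial need.

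An interval can be worked out afterwards from four counts, but its measure and method would then be chosen with the results in view, and in small tables that choice can change the message.

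**Working it through.** There is no power or precision calculation in the plan to reproduce. The only stated figure, 25 + 25 = 50, adds up.

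**Inputs**
- n = 25 per arm (Sample Size). This is a maximum, because of the 10-month stop.
- Pyelonephritis: Clinical Importance reports that "the incidence of pyelonephritis is only 2.4% when ASB is untreated compared to 0.6% when treated". These rates are for asymptomatic bacteriuria (ASB), so they are a proxy for sub-clinical bacteriuria (SCB). I keep their 4:1 ratio and vary the level.
- Cystitis: no rate is given. The Sub-Clinical Bacteriuria section says "It is also unknown the rate of progression from SCB to UTI and/or ASB". All cystitis rates and counts below are therefore assumptions.
- Assumed: two-sided 0.05, and chi-square without continuity correction.

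**1. Pyelonephritis: chance of an empty table**

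P(0 vs 0) = (1 - p1)^25 × (1 - p2)^25. At the cited rates this is 0.976^25 × 0.994^25 = 0.469.

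| Untreated vs treated (assumed for SCB) | P(no event in either arm) | P(at most 1 event in total) |
|---|---|---|
| 1% vs 0.25% | 73.1% | 96.1% |
| 2.4% vs 0.6% | 46.9% | 82.8% |
| 5% vs 1.25% | 20.3% | 53.3% |
| 10% vs 2.5% | 3.8% | 16.8% |

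With no event, the chi-square denominator is zero and there is no result. With one event, p = 0.31 whichever arm it falls in. If recruitment stops at 20 or 15 per arm, P(0 vs 0) at 2.4% vs 0.6% rises to 54.5% or 63.5%.

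Intervals can still be computed at 0 vs 0. The Clopper-Pearson upper limit for 0/25 is 1 - 0.025^(1/25) = 13.7%, and the Newcombe interval for the difference is -13.3 to +13.3 points.

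**2. Cystitis: what a p-value leaves out**

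Illustrative counts are 5/25 untreated and 3/25 treated.
- Chi-square = 50 × (5×22 - 3×20)² / (25 × 25 × 8 × 42) = 0.595, p = 0.44.
- Wilson limits: 5/25 gives 0.0886 to 0.3913, and 3/25 gives 0.0417 to 0.2996.
- Newcombe lower limit: 0.08 - √[(0.20 - 0.0886)² + (0.2996 - 0.12)²] = -0.131.
- Newcombe upper limit: 0.08 + √[(0.3913 - 0.20)² + (0.12 - 0.0417)²] = 0.287.

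The data would fit 29 fewer cystitis cases per 100 with treatment, or 13 more. The p-value shows neither.

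**3. Is chi-square itself unsound for cystitis?**

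Full enumeration of the 26 × 26 outcomes gives these true sizes at nominal 0.05:

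| Common rate | Chi-square | Fisher |
|---|---|---|
| 10% | 4.9% | 0.9% |
| 20% | 5.5% | 2.2% |
| 30% | 5.4% | 2.3% |
| 50% | 6.5% | 3.3% |

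Chi-square is close to nominal at 10% to 30%. Fisher's test has a price:

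| Untreated vs treated | Power, chi-square | Power, Fisher | Newcombe and Fisher disagree | Newcombe and chi-square disagree |
|---|---|---|---|---|
| 10% vs 5% | 8.1% | 1.3% | 2.8% | 4.0% |
| 20% vs 10% | 17.4% | 8.6% | 7.4% | 1.4% |
| 30% vs 15% | 25.7% | 15.0% | 10.6% | 0.1% |
| 40% vs 20% | 35.2% | 23.1% | 12.1% | <0.1% |

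**4. Does naming the method in advance matter?**

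At 8 vs 2, chi-square gives p = 0.034, Fisher gives p = 0.074, and the Newcombe interval is 1.5 to 44.4 points. With a continuity correction the interval becomes -1.4 to 46.5. Four defensible choices point in two directions.

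**The case against.** The best defence is that this is a 50-patient feasibility trial. It states no alpha, power or effect threshold, arm-level rates are already promised, and anyone can derive a risk difference and interval from the counts. No decision rule hangs on the choice of method. All of that is true, and it limits the consequence. It does not remove the gap: a trial that makes no claim to power is the one for which estimates matter most.

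A second objection is that the empty-table argument is thin. At 0 vs 0 Fisher's test returns p = 1, which says no more than an undefined chi-square, and the interval's width is fixed by n alone. That stands. The empty table shows that the planned test can fail, not that another test would rescue it. The gain comes from the interval.

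Third, an interval covers sampling error only. Under Methods, treated women are recultured after each round until clear, while untreated women have one scheduled test of cure. Later cultures follow clinical indication. Cystitis is defined by culture, so detection could differ by arm, and no interval corrects for that. This also stands.

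A reader might infer that chi-square is invalid at this sample size and should give way to Fisher's test throughout. The figures do not support that for cystitis: chi-square holds its size well at 10% to 30%, while Fisher's test roughly halves power at 20% vs 10% and conflicts with the Newcombe interval in 7% to 12% of trials at untreated rates of 20% to 40%.

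**Conclusion.** The concern holds as a gap in the analysis plan. Chi-square is the only between-arm analysis of the two incidences, and by itself it does not deliver the comparative objective. The change should be made, but the trial can run without it.

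The size of the pyelonephritis problem depends on a rate that the protocol does not know. The chance of no computable chi-square runs from about 4% to 73% over assumed untreated rates of 10% down to 1%. A reader might take the 47% as a forecast for this trial, but it rests on ASB rates and is one point in that range. The cystitis example is illustrative, since no rate is given.

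Two further inferences go beyond the documents. One is that the trial is at fault for being underpowered: it makes no power claim. The other is that an interval would settle whether to proceed: it supplies no criterion for that.

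**What to change.** Add to Data Analysis:

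> For cystitis and for pyelonephritis, the main result is the number and proportion with the event in each randomised arm, with a Clopper-Pearson 95% CI, and the risk difference (no treatment minus treatment) with a Newcombe hybrid-score 95% CI without continuity correction. P-values are secondary and exploratory: Pearson chi-square without continuity correction for cystitis, and the two-sided Fisher's exact test for pyelonephritis, where counts are expected to be too sparse for chi-square. If an interval and a p-value disagree, the interval prevails. The intervals reflect sampling error only and do not account for differences in culture follow-up between the arms.

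The cost is a few sentences and standard software, with no new data, visits or patients. The downsides are modest. The intervals will be wide. Newcombe coverage is slightly low at high event rates (94.6% at 30% in both arms, 93.5% at 50%). Fisher's test is conservative, which matters little for an exploratory p-value on a rare outcome.

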Patients meeting clinical indications will have a urine culture ordered due to two reasons: a) symptoms of a UTI or b) positive UA suspicious for infection/inflammation. A negative urine analysis is defined as an analysis that is negative for bacteria, leukocyte esterase, nitrites, and protein. A negative urine culture is defined as no growth or any amount of skin flora only.

Inclusion Criteria:

We will include pregnant women who seek prenatal care within the University of Texas Health System with UT Physicians.

Exclusion Criteria:

We will exclude women:

- Less than 18 years of age
- Risk factors to complicated UTI (including but not limited to: diverticula, urolithiasis, renal cysts, indwelling catheter, intermittent catheterization, stent placements, nephrostomy tubes, neurogenic bladder, cystocele, vesicoureteral reflux, ileal conduit)⁸
- Use of immunosuppressant drugs
- Abnormalities of the urinary tract (including but not limited to: known ureteric or urethral strictures, tumors of the urinary tract, pelvicalyceal obstruction, congenital anomalies, history of urological procedures)
- History of renal disease including renal failure and transplants
- Urine culture $> 10^5$ CFU of any organism

Those with a urine culture for bacteria but $1-10^5$ CFU will be randomized to one of two management plans:

1. Prenatal care with treatment for any urine culture with growth of $1-10^5$ CFU of any organism
2. Prenatal care without treatment for any urine culture with growth of $1-10^5$ CFU of any organism

Randomization:

Randomization will be performed based on a computer-generated list that will be created by a non-clinical member of the research team. Randomization will be stratified by clinic site. A permuted block randomization with a random fashion will be used to prevent imbalances between sites. At subsequent clinic visits, clinic staff will continue to obtain urine culture from symptomatic patients or patients where further work up of a urine culture is warranted. 'Physician to treat urine culture with $1-100,000 (10^5)$ CFU" or 'Physician to NOT treat urine culture with $1-100,000 (10^5)$ CFU", based on the computer-

generated list, stored on the RedCap database. The research nurses and team may access the RedCap database from any clinical site.

Methods:

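### Randomisation is stratified by clinic site but the planned chi-square test ignores site; this is conservative and costs some power only if event rates differ widely between sites

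*Combined protocol and SAP*

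**What the plan says.** Under Randomization: "Randomization will be stratified by clinic site", and "A permuted block randomization with a random fashion will be used to prevent imbalances between sites". No block size is given.

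Under Data Analysis, the comparative methods are two sentences: "Chi-square tests will be used to compare categorical data between the two treatment groups" and "Student's t-test will be used to compare numerical data". Neither names site, a stratified test or an adjusted estimate. The section states no significance level, sidedness or confidence interval, and does not say whether the chi-square carries a continuity correction.

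Under Sample Size: "Because this is a feasibility trial, 50 patients will be recruited from all clinical sites", 25 to each arm. The number of sites is not stated. Data Collection names two clinic schedules as sources: "Information for these forms will be obtained from UTPB and Bellaire clinical schedule, Care4 and AllScripts".

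The Primary Outcome section describes binary events: a culture above 10^5 "at any point during antenatal care in this pregnancy population and the incidence of pyelonephritis". The chi-square sentence is therefore the one that governs the primary comparison.

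**The concern.** Blocking within site makes the arms nearly equal in number at each site. Differences in event rate between sites then largely cancel out of the treatment contrast. The unstratified chi-square takes its variance from the pooled event rate, which still contains the between-site spread. If sites differ, the test works with too large a standard error and its true type I error falls below nominal.

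A difference between sites is possible here. The Background describes strong variation in clinicians' practice, and Methods leaves follow-up cultures after randomisation to clinical indication. Because the primary outcome counts a positive culture at any time in antenatal care, local habits in ordering cultures can affect how many events are found. At stake is part of the value of the stratification, in a trial of 50 women that is meant to inform whether a larger one is needed.

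**Working it through.** **No stated figure to reproduce.** The sample size of 50 rests on feasibility alone, with no significance level, power or effect size. The check is therefore of the planned test under assumed conditions.

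**Inputs from the document.** 50 women, 25 per arm; allocation stratified by site in permuted blocks; binary primary outcome; unstratified chi-square.

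**Assumptions.** Two sites (suggested by the two named schedules), with 13 + 13 and 12 + 12 women by arm, so full balance within site; two-sided 5%; no continuity correction on either test; the site event rates shown. For power, the site rates apply to the control arm, and a common odds ratio of 0.2 gives the treated rates.

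**Step 1: standard error of the risk difference with no treatment effect.**

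- Variance assumed by the unstratified test: p(1 − p)(1/25 + 1/25), with p = (26·pA + 24·pB)/50.
- Actual variance under balanced, site-stratified allocation: 2[13·pA(1 − pA) + 12·pB(1 − pB)]/25².

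At 10% and 50%:
- p = (2.6 + 12)/50 = 0.292
- assumed variance = 0.292 × 0.708 × 0.08 = 0.01654, SE 0.1286
- actual variance = 2(1.17 + 3.00)/625 = 0.01334, SE 0.1155
- ratio of SEs = 1.11

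At 10% and 30%:
- p = (2.6 + 7.2)/50 = 0.196
- assumed variance = 0.196 × 0.804 × 0.08 = 0.01261, SE 0.1123
- actual variance = 2(1.17 + 2.52)/625 = 0.01181, SE 0.1087
- ratio of SEs = 1.03

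The same formulas give 1.01 at 10% and 20%, and 1.24 at 5% and 60%.

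**Step 2: size and power.** All outcomes of the four site-by-arm binomial counts were enumerated exactly. Rejection probabilities were summed for the Pearson chi-square and for the CMH test stratified by site.

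| Site rates | SE ratio | Size, chi-square | Size, CMH | Power, chi-square | Power, CMH |
|---|---|---|---|---|---|
| 10% / 20% | 1.01 | 5.2% | 5.1% | 27.8% | 27.8% |
| 10% / 30% | 1.03 | 4.7% | 4.8% | 37.1% | 37.2% |
| 20% / 40% | 1.02 | 4.8% | 4.8% | 52.9% | 52.1% |
| 10% / 50% | 1.11 | 3.1% | 4.9% | 46.3% | 48.8% |
| 20% / 70% | 1.16 | 3.1% | 4.7% | 54.3% | 61.5% |
| 5% / 60% | 1.24 | 1.6% | 4.8% | 41.0% | 50.0% |
| 30% / 30% | 1.00 | 5.4% | 4.9% | 55.3% | 53.6% |

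**Step 3: reading the table.** Up to a gap of about 20 points the tests are practically the same; at 10% and 30% with no effect, they disagree in under 0.4% of trials. At gaps of 40 points or more the chi-square is clearly conservative, and CMH gains roughly 2 to 9 points of power in the cases shown. With equal rates of 30%, CMH loses 55.3 − 53.6 = 1.7 points. Wherever the site rates differ, chi-square size is at most 5.2%.

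**Step 4: site sizes.** With sites of 36 and 14 the pattern holds: chi-square size is 4.8% at 10% and 30%, and 3.3% at 10% and 50%.

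**The case against.** The strongest case against is that the effect needs site gaps for which the documents give no evidence. All women come from one provider group under the same exclusions, and the Background calls the progression rate unknown. The only outcome rates quoted, 2.4% and 0.6% for pyelonephritis in untreated and treated asymptomatic bacteriuria, are far below those at which site matters. At assumed site rates of 2% and 6% both tests have size 1.1%.

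The trial is also a pilot with little power by either test: about 16% for 20% against 10% at 25 per arm, two-sided 5%. Sparse data may matter more than site, since the expected events per arm fall below 25 × 0.20 = 5 once the pooled rate is under 20%, and splitting by site makes cells sparser still. All of this stands and limits the weight of the point. It does not remove the mismatch between design and analysis.

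Two stronger readings are tempting, and the documents support neither. A reader might infer that the plan's stated error bars are wrong. The plan states no standard error or interval, so there is none to be wrong. A reader might also infer that the analysis is invalid whenever sites differ at all. Any difference has an effect in principle, but for gaps of 10 to 20 points it is 1% to 3% of the standard error, and its direction is conservative.

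**Conclusion.** The mismatch is real: site governs the randomisation and is absent from the analysis. Its consequence is lost precision if site event rates are far apart, without meaningful false-positive inflation.

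The figures rest on an assumed two-site layout, full balance within site, a two-sided 5% level and invented site rates. Incomplete blocks would weaken the conservative effect. Since the documents give none of these quantities, the actual loss cannot be stated; it may be nil. Severity is minor, and the change is an optional improvement.

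**What to change.** In Data Analysis, for the primary outcome, replace the unstratified chi-square with a CMH test stratified by clinic site. Report the Mantel-Haenszel risk difference with its 95% confidence interval. Specify an exact stratified version for sparse events, and set in advance when it applies. If the sponsor prefers to leave site out, the plan should give the reason.

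The cost is a sentence or two. Site is already needed to run the randomisation, so no new data are collected. The statistical price is up to about 2 points of power if the sites turn out to have the same event rate, as in the 30% / 30% row above.
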